#### *Statistical Analysis*

For the baseline data, continuous variables were compared with the two-sample t-test and categorical variables were compared with Fisher's exact test or a chi-square test.

For the primary outcome (value, ratio of ADLS to cost), the Wilcoxon rank sum test was used to compare between the Control Group and interACTION Group. P-Values below \* $p=0.05$  were considered statistically significant for all outcomes. For the remainder of the cost analyses parameters (weeks of physical therapy, number of physical therapy visits, and total cost), a two-sample t-test was used to compare between groups.

For other clinical outcomes data, if the distribution was normal at each time point, then a repeated measures ANOVA was used. A repeated measures ANOVA was used to compare difference between groups for the ADLS, Passive ROM (flexion), and Active ROM (flexion). Otherwise, if some time points had normal data and others did not then a two-sample t-test was used for normally distributed data and the Wilcoxon rank sum test was used for non-normally distributed data.

For the functional performance tests that were assessed at the 5- and 10-week visits, a z-score (or standard score) was used to calculate a cumulative score for the Six-minute Walk Test (distance in feet), Stair Climb Test (time divided by steps), TUG (time), and Surgical Unilateral Balance (time). The z scores are the average of the z scores for each of the functional tasks. On average, the z scores are close to zero, meaning that the overall individuals within the group, the scores for each subject are not different than the mean score across all subjects.

Differences between the cumulative z-scores were assessed using a two-sample t-test.

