### *Methods*

Sixty patients following total knee arthroplasty will be monitored for up to 10 weeks during their outpatient physical therapy course. For the control group, 30 of these patients will undergo two to three weekly sessions with a physical therapist supplemented by unmonitored home-based exercises. The second group of 30 patients will fulfill their rehabilitation course with one to three sessions per week with a physical therapist and will use the interACTION home rehabilitation monitoring program to supplement these sessions. The patients in the interACTION group will use the device for the first two weeks of their rehabilitation in the clinic in order to become familiar with the device before home use. After the first two weeks the patient will be asked to take the device home and reduce their weekly outpatient visits by one visit per week. However, if the physical therapist feels it is best for the patient to deviate from the protocol, this is allowed. At the end of the 10-week rehabilitation course, rehabilitation compliance, costs, and patient outcomes will be analyzed for differences between the two groups.

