## **Methods**

For this randomized treatment study, we will recruit 60 patients that have undergone total knee arthroplasty (TKA) that are being referred for post-operative outpatient physical therapy. After obtaining informed consent, and upon successful

screening/recruitment, subjects will be randomly assigned to one of two groups:

1. Control Group: Rehabilitation performed by a physical therapist and supplemented with a home exercise program for a maximum of ten weeks. Therapy will consist of two to three visits per week as prescribed by the physical therapist and based on the best interest of the patient. Patients will record their performance of the prescribed home exercise programs on a paper-based exercise log on a daily basis.
2. InterACTION Intervention Group: Rehabilitation performed by a physical therapist and supplemented by use of interACTION for a maximum of ten weeks. This will include two to three visits per week for two weeks in which the patient will use interACTION during routine outpatient physical therapy sessions to familiarize them with the system. After two weeks, the patient will be issued an interACTION device for home use that will guide them through their exercise program. At this point subjects in the interACTION group should continue to return to the outpatient rehabilitation facility, but reduce their weekly routine visit with their physical therapist by one during the next eight weeks of recovery, while concurrently using interACTION at home. Patients who attended two visits per week for the first two weeks should subsequently attend one visit per week. Patients who attended three visits per week for the first two weeks will subsequently attend one to two visits per week. However, if the physical therapist feels it to be in the best interest of the patient to deviate from the protocol, this is allowed.

*Note: InterACTION is currently under development, not a commercial application. The 3rd Party Developer was OpenArc, LLC ([name]). The mobile application is currently supported on a Nexus tablet with Android operating system (specifically lollipop and kitkat versions). The mobile application and the kinematic sensors will be provided to the participant, the participants will NOT use a personal device.*

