Rehabilitation Compliance will be evaluated by the study team through the use of home exercise logs and interACTION reports. Logs will be reviewed at the follow-up visits with the research team. Outcome measures will be collected at baseline, 5 weeks (+/- 7 days) after enrollment, and upon discharge or a maximum of 10 weeks (+/- 7 days) after enrollment.

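### The primary value test and the cost tests make no use of baseline ADLS, so some precision and protection against chance imbalance are given up; the tests remain valid and the loss may be small

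*Combined protocol and SAP*

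**What the plan says.** All references are to the combined protocol and SAP.

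- **Primary test (Statistical Analysis):** "For the primary outcome (value, ratio of ADLS to cost), the Wilcoxon rank sum test was used to compare between the Control Group"; the other arm is interACTION. No covariate, stratification factor or adjusted sensitivity analysis is named. The text does not say whether the ADLS in the ratio is the final score or the change from baseline.
- **Cost parameters (same section):** "weeks of physical therapy, number of physical therapy visits, and total cost), a two-sample t-test was used to compare between groups".
- **Baseline tests (same section):** "For the baseline data, continuous variables were compared with the two-sample t-test". ADLS is not named there, but it is a continuous variable.
- **Other use of ADLS (same section):** it is analysed as a clinical outcome by repeated measures ANOVA. The time points in that model are not listed.
- **Schedule (Methods):** "Outcome measures will be collected at baseline, 5 weeks (+/- 7 days) after enrollment", and again at discharge or at most 10 weeks. The Outcomes list includes ADLS with no visit restriction, so a baseline reading is planned.
- **Design:** 60 patients, 30 per arm (Methods in the Abstract). Methods describes random assignment to two groups and no balancing factor. Purpose calls the trial a pilot.

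**The concern.** Baseline ADLS is the baseline of the primary outcome's own numerator. It may also bear on the denominator, if patients with better function at the start finish therapy sooner. A covariate that predicts the outcome, used in the analysis, removes part of the residual variance and corrects for chance differences between arms. The plan schedules the reading and then leaves it out of the primary and cost comparisons.

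The baseline significance tests do not fill the gap. Under randomisation their null hypothesis is true by design, and a non-significant result leaves whatever imbalance exists in the data. With 30 per arm and no stratification described, the primary comparison has no other variance reduction. At stake are some power, and a primary result that a chance baseline difference can move in either direction.

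**Working it through.** **Inputs.** From the documents: 30 per arm, and a 0.05 threshold that applies to every outcome ("were considered statistically significant for all outcomes"). Sidedness is not stated; two-sided is assumed. The documents give no effect size, SD, power or correlation, so there is no planned figure to reproduce. Let rho be the correlation of baseline ADLS with the value ratio; every rho below is an assumption.

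**1. Power without adjustment.** For a two-sample t-test with 58 df, noncentrality = d × sqrt(30/2). With d = 0.737 this is 0.737 × 3.873 = 2.854, and power is 80.1%.

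**2. Power with adjustment.** The residual SD falls by the factor sqrt(1 − rho²), so d becomes d / sqrt(1 − rho²), with 57 df.

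| rho | 1 − rho² | adjusted power | gain (points) |
|---|---|---|---|
| 0.1 | 0.99 | 80.5% | 0.4 |
| 0.2 | 0.96 | 81.7% | 1.6 |
| 0.3 | 0.91 | 83.7% | 3.5 |
| 0.4 | 0.84 | 86.5% | 6.3 |
| 0.5 | 0.75 | 90.0% | 9.8 |

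**3. Rank version.** In a simulation (8,000 runs, log-normal ratio, effect 0.74 SD on the log scale), Wilcoxon against Quade's rank ANCOVA gave 78.3% v 81.6% at rho 0.3, 78.1% v 83.5% at 0.4 and 77.7% v 86.8% at 0.5. Type I error of the rank ANCOVA was 4.7–5.0%. The gains are close to those in the table.

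**4. Which rho is plausible if cost is unrelated to baseline function?** To a log-scale approximation, rho = r × CV(ADLS) / sqrt(CV(ADLS)² + CV(cost)²), where r is the correlation of baseline with final ADLS. With r = 0.5 assumed:

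- equal CVs: 0.5 / sqrt(1 + 1) = 0.35, gain about 5 points
- cost CV 1.5 times as large: 0.5 / sqrt(1 + 2.25) = 0.28, gain about 3 points
- cost CV twice as large: 0.5 / sqrt(1 + 4) = 0.22, gain about 2 points

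A wider simulation (2,000 runs per setting, ADLS CV 0.15–0.20, cost CV 0.20–0.50, r 0.3–0.7, cost independent of baseline) gave rho of about 0.09–0.47 and gains of about 0 to 8 points. Gains were under about 3 points at cost CV 0.50.

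**5. If better baseline function goes with lower cost.** With ADLS CV 0.2, cost CV 0.5 and r = 0.5 (6,000 runs), Wilcoxon against rank ANCOVA gave:

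- baseline–cost correlation 0: 78.8% v 79.5%
- −0.2: 78.3% v 82.9%
- −0.3: 78.8% v 85.1%
- −0.4: 78.9% v 88.8%

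**6. Chance imbalance.** The standard error of the baseline difference, in SD units, is sqrt(2/30) = 0.258. The largest difference that is not significant is 2.002 × 0.258 = 0.517 SD, so 0.5 SD would pass the baseline test. A difference at least that large has z = 0.5 / 0.258 = 1.94, a probability of about 5%.

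Given a 0.5 SD imbalance and no treatment effect, the unadjusted statistic is approximately normal with mean rho × 0.5 × sqrt(15) and SD sqrt(1 − rho²):

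- rho 0.3: mean 0.581, SD 0.954. Upper tail beyond (1.96 − 0.581) / 0.954 = 1.446 is 7.4%; the lower tail adds 0.4%. Total 7.8%.
- rho 0.5: mean 0.968, SD 0.866. Upper tail beyond (1.96 − 0.968) / 0.866 = 1.145 is 12.6%; the lower tail is negligible. Total 12.6%.

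At the median absolute imbalance, 0.6745 × 0.258 = 0.17 SD, the same calculation gives 4.4% (rho 0.3) and 3.4% (rho 0.5), below nominal.

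**The case against.** The strongest reply is that an unadjusted rank test in a randomised pilot is sound, and that the benefit of adjusting is unknown.

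- **Validity.** Averaged over randomisations the Wilcoxon test keeps its 5% level. A reader might infer from the 8% and 13% figures that the false-positive rate is inflated. It is not: those figures hold only given an imbalance that is uncommon. This stands.
- **Size.** Cost has no baseline and may dominate the variance of the ratio, so rho could be 0.2 or lower and the gain a point or two. Nothing in the documents states that baseline function predicts when therapy ends. Methods leaves visit frequency to the therapist and lowers it by design in the interACTION arm. The reply that discharge timing and visit numbers feed into cost is reasonable but remains an assumption. A reader might infer that material power is certainly lost; the documents do not support that.
- **Use of baseline ADLS.** A reader might infer that baseline ADLS serves only for a significance test. The repeated measures ANOVA of ADLS contradicts that, since baseline is plausibly one of its time points. The supportable statement is narrower: baseline ADLS is absent from the primary and cost tests.
- **Numerator.** If the ratio uses change in ADLS, baseline already enters it and the rho values above do not carry over, although adjustment could still help.
- **Timing.** Statistical Analysis is written in the past tense, so analysis may be complete. Replacing the primary test would then be post hoc.

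None of this gives a reason to leave out a planned covariate that costs one degree of freedom.

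**Conclusion.** The point holds as a minor improvement. It concerns precision and conditional imbalance in the primary and cost comparisons, not the validity of the tests, and it leaves the ADLS, range-of-motion and functional analyses aside.

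The likely gain is about 0 to 5 points of power if cost is unrelated to baseline function, and more if patients with better baseline function finish therapy sooner. These figures assume a two-sided 5% test, all 30 patients per arm analysed, and an effect that the unadjusted test detects with 80% power. The documents supply neither the effect nor rho. The pilot makes no power claim that this would undermine.

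**What to change.** 1. State whether the numerator of value is final ADLS or change in ADLS, and at which visit.
2. Make the primary test a rank ANCOVA (Quade): regress ranked value on ranked baseline ADLS and compare the residuals between arms. Keep the unadjusted Wilcoxon test as a sensitivity analysis.
3. Use ANCOVA with baseline ADLS for weeks of therapy, visits and total cost, with the t-tests as sensitivity analyses.
4. Regression of log value on arm and baseline ADLS is an alternative, not an equivalent: it estimates a ratio of geometric means and works only if every ratio is positive, which a change score may not ensure.
5. Use the baseline reading taken before allocation where there is one; the documents do not place baseline relative to randomisation. Say how a missing baseline is handled, for example by mean imputation.
6. Replace the baseline significance tests with a descriptive table.
7. If the analysis is already done, leave the unadjusted result as the primary one and report the adjusted result beside it, labelled as added.

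The cost is SAP wording and one degree of freedom out of 58. No extra data are needed, provided a pre-allocation baseline reading exists.

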### *Outcomes*

- Range of motion—Active and passive range of motion (ROM) will be measured with a standard goniometer while the patient lies in the supine position. Extension and flexion of each knee will be measured. Extension will be measured passively with a quad set and actively during a straight leg raise. The range of extension and flexion will be expressed as the difference between the involved and non-involved knees.
- Numeric Pain Rating Scale—Subjects will be asked to rate their level of pain currently and their level of worst & least pain in the past 24 hours on a scale from 0 (no pain) to 10 (worst pain imaginable).
- Activities of Daily Living Scale of the Knee Outcome Survey (ADLS)—The ADLS is a 14-item measure of symptoms and activity limitations for

individuals with a variety of knee impairments.

- Veterans RAND 12-Item Health Survey (VR-12)—The VR-12 is a 12-item patient-reported general measure of health-related quality of life that was adapted and developed from the RAND 36-Item Health Survey at the RAND Corporation and Medical Outcomes Study.
- Functional performance will also be tested in all patients. The following functional tests will be assessed at 5- and 10-week visits:
  - Six-minute Walk Test to assesses the subject's ability to walk community distances. The subject is asked to walk as far as possible in six minutes on a closed course with standing rest breaks as needed. The patient is free to use their preferred assistive device.
  - The Stair Climbing Test to test basic daily function in which a patient ascends and descends a standard flight of stairs as quickly and safely as possible, using their preferred gait pattern, assistive device, and hand rail.
  - The Timed Up and Go Test (TUG) in which the patient sits in a standard armed chair, rises, walks three meters, turns around, walks back to the chair and sits. Excessive time to complete the TUG can indicate mobility impairments and potential fall risks in elderly patients.
  - The Unilateral Balance Test in which the patient attempts to maintain single leg balance for up to two minutes, with the test ending when the patient loses balance enough to put the opposite foot on the ground.

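### The plan calls every outcome with p below 0.05 statistically significant, over about 18 to 23 between-group tests, without adjustment, ordering or an exploratory label

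*Combined protocol and SAP*

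**What the plan says.** The Statistical Analysis section identifies a single primary analysis: "For the primary outcome (value, ratio of ADLS to cost), the Wilcoxon rank sum test was used" to compare the two groups. The next sentence sets the threshold, under which p-values below 0.05 "were considered statistically significant for all outcomes".

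The section then lists further between-group comparisons:
- t-tests on three cost parameters;
- repeated measures ANOVA for ADLS, passive flexion and active flexion;
- a t-test on the cumulative functional z-score, whose component tests are done at 5 and 10 weeks.

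For a clinical outcome that is normal at some time points and not at others, "a two-sample t-test was used for normally distributed data and the Wilcoxon rank sum test was used for non-normally distributed data", which means a separate test at each time point.

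The Outcomes section adds measures that are not among the three named under ANOVA. Patients "rate their level of pain currently and their level of worst & least pain in the past 24 hours". For the knee, "Extension will be measured passively with a quad set and actively during a straight leg raise". The VR-12 is also collected, and the number of scores to be analysed is not given. The Purpose section of the Abstract calls the trial a pilot study.

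**The concern.** This is a stated decision rule, not a missing detail. Naming a primary outcome protects that one test. The threshold sentence then lets every other comparison be called significant on the same terms, and testing by time point increases the number of comparisons. Nothing elsewhere in the document limits the rule.

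An isolated p of 0.04 on one pain rating, at one visit, could therefore be described as a statistically significant benefit of the device, whatever the primary outcome shows. The Potential Benefits section links improved outcomes in this trial to future use of the device, so such a claim would carry weight.

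**Working it through.** The documents give no familywise error rate and no number of tests, so there is no figure of the plan's own to reproduce. A single test at 0.05 has a 5% error, as stated.

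**Step 1. Count the tests.** Fixed items, from Statistical Analysis:
- value: 1
- weeks of therapy, number of visits, total cost: 3
- ANOVA for ADLS, passive flexion, active flexion, one group comparison each: 3
- functional z-score at two visits: 2

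Subtotal: 1 + 3 + 3 + 2 = 9.

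Items tested at the two post-baseline visits (5 weeks, and discharge or 10 weeks). That these outcomes are tested by visit is an assumption, made because they are not among the three named under ANOVA:
- extension, passive and active: 2 × 2 = 4
- pain now, worst, least: 3 × 2 = 6
- VR-12, one or two scores (assumed): 2 or 4

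Total: 9 + 4 + 6 + 2 = 21, or 9 + 4 + 6 + 4 = 23.

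**Step 2. Set aside comparisons expected to differ by design.** The Methods section asks the interACTION group to attend one visit fewer per week after week 2. Visits, and through them total cost and value, may truly differ, and a real difference is not a false positive. Removing these three leaves 21 − 3 = 18 or 23 − 3 = 20.

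**Step 3. Chance of at least one false positive, all remaining nulls true.** For k independent tests:
- in either direction: 1 − 0.95^k
- favouring the device, with two-sided tests: 1 − 0.975^k

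For tests with a common correlation ρ (z-statistics oriented so that positive favours the device, c = 1.96), the chance in either direction is 1 − ∫ φ(g) [Φ((c − √ρ g)/√(1−ρ)) − Φ((−c − √ρ g)/√(1−ρ))]^k dg. Dropping the second Φ term gives the chance of a result favouring the device. The value ρ = 0.5 is an assumption.

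| Tests | Independent, either direction | Independent, favouring device | ρ = 0.5, either direction | ρ = 0.5, favouring device |
|---|---|---|---|---|
| 18 | 60% | 37% | 40% | 20% |
| 20 | 64% | 40% | 42% | 21% |
| 21 | 66% | 41% | 43% | 22% |
| 23 | 69% | 44% | 45% | 23% |

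The expected number of false positives does not depend on the correlation: 0.05 × 18 = 0.9 to 0.05 × 23 = 1.15.

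**Step 4. Sensitivity, either direction.**
- 23 tests: 58% at ρ = 0.3 and 31% at ρ = 0.7.
- 23 tests with correlation 0.5 to 0.7 within a domain and 0.1 to 0.3 between domains: 50% to 62%.
- Every clinical outcome through one ANOVA, with two VR-12 scores: 1 + 3 + 3 + 2 + 3 + 2 + 2 = 16 tests, giving 56% if independent and 37% at ρ = 0.5.

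**The case against.** The best reply is that this is a 60-patient pilot with one named primary outcome, where unadjusted secondary p-values are common and readers discount them. The threshold sentence sets a per-test cut-off. Nothing says that a secondary result can establish success or stand in for a null primary. This stands in part: it makes the problem one of labelling, not of the primary inference. It does not remove the rule, because the plan gives the significance label to all outcomes, and a pilot is where an exploratory label fits best.

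A second reply is that independence is contradicted by the plan itself. Value is built from ADLS and cost, visits drive cost, the three pain ratings come from one scale, and measures are repeated over visits. This stands. The independence figures are an upper figure only.

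A reader might also infer a count of 30 tests by including all three time points. That adds 2 + 3 + 2 = 7 baseline comparisons to the 23, and a baseline difference cannot be reported as a device effect.

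Finally, the section is written in the past tense, which suggests that the analyses may already have been run. If so, the change affects how results are described, and that is still open to correction.

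**Conclusion.** The concern holds as a fault in the decision rule. With 18 to 23 post-baseline tests and all their nulls true, the chance of at least one nominally significant result is about 40% to 45% at a common correlation of 0.5, and at most 60% to 69% under independence. For a false result favouring the device it is about 20% to 23%, and at most 37% to 44%. These figures rest on one or two VR-12 scores, on separate testing of extension, pain and VR-12 at two visits, on two-sided tests for the directional figures, and on a correlation that the documents do not give. Even at correlation 0.7 with 23 tests, the either-direction chance is 31%, about six times the nominal 5%.

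Two stronger readings are not supported. One is that a false claim is more likely than not: this depends on a correlation that is unknown, fails at 0.5 for these counts, and does not hold for false benefit claims even under independence. The other is that the primary result is compromised: the single primary test keeps its own 5% error.

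**What to change.** Replace the threshold sentence in Statistical Analysis with wording to this effect: only the primary outcome, value, is tested at two-sided 0.05 and may be described as statistically significant; every other outcome is reported as a between-arm difference with a 95% confidence interval and a nominal p-value, and is labelled exploratory. State also how many VR-12 scores are analysed and at which visits each outcome is compared, so that the number of tests is known.

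The cost is a change of wording. No alpha is spent, no analysis is dropped and the sample size does not change. The downside is that secondary results can no longer be described as statistically significant. If the analyses have already been run, the same rule can be applied when the results are reported.

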#### *Potential Benefits*

This study aims to increase knowledge related to use of the interACTION device to supplement post-operative rehabilitation after TKA. If the interACTION device leads to improved post-operative outcomes, patients in the future would benefit from use of the device to supplement their post-operative rehabilitation program. If beneficial, use of the interACTION device would result lead to the same or better outcomes with fewer in-clinic physical therapy visits, thus improving the value of care with lowered healthcare costs and expenditures.

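### ADLS, ROM, pain and VR-12 have a collected baseline but no stated baseline covariate; the ANOVA names neither visits nor tested term, and an undefined normality check chooses the test visit by visit

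*Combined protocol and SAP*

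**What the plan says.** On timing, the Methods section states: "Outcome measures will be collected at baseline, 5 weeks (+/- 7 days) after enrollment", with a last assessment at discharge or at 10 weeks at the latest. Under Outcomes, only the functional tests are given a narrower schedule: "The following functional tests will be assessed at 5- and 10-week visits". ADLS, ROM, pain and VR-12 therefore have a planned baseline value and two follow-up values.

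Under Statistical Analysis, the only stated use of baseline data is a set of between-group tests. For the other clinical outcomes, "if the distribution was normal at each time point, then a repeated measures ANOVA was used", and for three of them the method is named: "A repeated measures ANOVA was used to compare difference between groups for the ADLS, Passive ROM (flexion), and Active ROM (flexion". The alternative branch reads: "Otherwise, if some time points had normal data and others did not then a two-sample t-test was used for normally distributed data", with the Wilcoxon rank sum test for the rest. P-values below 0.05 "were considered statistically significant for all outcomes". No effect estimate or confidence interval is named for these outcomes.

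**The concern.** Three things are left open.

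- **Baseline.** No covariate is stated. If baseline were a response level and group-by-time the tested term, the ANOVA would compare changes and so use baseline indirectly. The text does not say this, and it is not the same as covariate adjustment.
- **Contrast.** The ANOVA sentence does not say which visits enter, whether group or group-by-time is tested, or which visit carries the conclusion. Two analysts could report different ADLS tests from the same data.
- **Choice of test.** Normality has no criterion. In the mixed case, one outcome can be reported as a mean difference at one visit and as a rank comparison at the other. No branch is given for an outcome that is non-normal at every visit.

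Under Potential Benefits, the hope is for "the same or better outcomes with fewer in-clinic physical therapy visits". The outcome half of that statement rests largely on these measures. A reader will want a defined difference and its precision, which a p-value from an unnamed contrast does not give.

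**Working it through.** The documents give no power, SD, effect size or correlation, so there is no figure of the plan to reproduce. What follows is illustrative.

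**Inputs from the documents.** 60 patients, 30 per arm (Abstract and Methods); baseline and two follow-ups (Methods); 0.05 threshold (Statistical Analysis).

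**Assumptions.** Two-sided testing, complete data, SD 1, effect 0.5 SD, and correlation r = 0.3/0.5/0.7 between all pairs of visits unless stated otherwise.

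**Formula.** Power comes from the noncentral t, with noncentrality = effect/√V × √(30/2) and 58 df (57 with the covariate). CI half-width = t(0.975) × √(V × 2/30).

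**One visit, like for like**
- Unadjusted: V = 1, noncentrality 0.5 × 3.873 = 1.936, power 48%, half-width 2.002 × 0.258 = 0.52 SD.
- Adjusted: V = 1 − r² = 0.91/0.75/0.51, noncentrality 2.03/2.24/2.71, power 51/59/76%, half-width 0.49/0.45/0.37 SD.
- At r = 0.2: V = 0.96, power 49%, half-width 0.51 SD. The gain at r = 0.2–0.3 is therefore 1–3 points.

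**Readings that the ANOVA sentence allows, against adjusted analyses (constant effect at both follow-ups)**

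| Analysis | Effect | V | Power at r = 0.3/0.5/0.7 |
|---|---|---|---|
| Group, mean of three visits | 2 × 0.5/3 = 0.333 | (1+2r)/3 = 0.53/0.67/0.80 | 41/34/29% |
| Group, mean of two follow-ups | 0.5 | (1+r)/2 = 0.65/0.75/0.85 | 66/59/54% |
| Mean change from baseline | 0.5 | (1+r)/2 + 1 − 2r = 1.05/0.75/0.45 | 46/59/81% |
| Group-by-time, 2 df | (0, 0.5, 0.5) | noncentral F(2,116), λ = 2.5/(1−r) = 3.57/5.00/8.33 | 37/49/72% |
| Adjusted mean of two follow-ups | 0.5 | (1+r)/2 − r² = 0.56/0.50/0.36 | 72/77/89% |
| Adjusted final visit | 0.5 | 1 − r² = 0.91/0.75/0.51 | 51/59/76% |

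For the mean of two follow-ups, the covariate adds 6 points at r = 0.3 (66 to 72%), 17 at 0.5 (59 to 77%, rounded) and 35 at 0.7 (54 to 89%). Against the best unadjusted reading in each column (66/59/81%) the gain is 6/17/8 points. With baseline correlation 0.2–0.3 and follow-up correlation 0.7 it is only 2–5 points.

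**Final visit or mean?** Under a constant effect, the adjusted final visit does not beat the best unadjusted reading: 51 vs 66%, 59 vs 59%, 76 vs 81%. If the effect appears only at the final visit, the order reverses under equal correlations: adjusted final visit 51/59/76%, 2-df group-by-time 37/49/72%, adjusted mean 25/27/35%. With baseline correlation 0.2–0.3 and follow-up correlation 0.7, the 2-df test leads in that case, at 62–63% against 49–51%.

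**Open contrast (simulation, 20,000 trials per setting).** With a constant 0.5 SD effect, three readings (group over three visits, group over two follow-ups, mean change) disagree on significance in 56/58/66% of trials. If only follow-up mean and change are counted, the figure is 39/38/42%. Under the null, significance at either follow-up occurs in 8.2–9.3% (1 − 0.95² = 9.75% if independent), and the best of the three readings is significant in 10.7–11.1%.

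**Normality rule (assumed Shapiro-Wilk at 0.05, 60 pooled values).** Exactly normal data fail at one or more of three visits with probability 1 − 0.95³ = 14.3% if independent (simulated 14–15%). The two follow-ups get different tests with probability 2 × 0.05 × 0.95 = 9.5% if independent (simulated about 9%).

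**The case against.** The strongest reply is that nothing here is invalid. Randomisation protects unadjusted follow-up comparisons, and each single test keeps about 5% error. That stands: the missing covariate costs efficiency and leaves chance baseline imbalance uncorrected, but it does not bias the comparison on average.

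Second, the gain at one visit is measured against a t-test, which the plan uses only in its alternative branch and not for ADLS or flexion. That also stands, so the gain of 28 points at r = 0.7 (48 to 76%) must not be read as what the plan loses on ADLS. The table gives the comparison with the ANOVA readings.

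Third, a reader might infer that the final visit is plainly the right single contrast, because "After two weeks, the patient will be issued an interACTION device for home use that will guide them through their exercise program", so that week 5 reflects only about three weeks of home use. The documents do not settle it. The final visit falls at discharge or week 10, its timing may differ by arm, and weeks of therapy is itself a compared outcome. The power figures point both ways.

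Fourth, a reader might infer that the normality rule inflates type I error. That is not shown. The 8–11% figures come from testing two visits or choosing among contrasts. The rule mixes scales within an outcome. For ADLS and flexion, the text has already settled on the ANOVA.

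Fifth, the statement under Potential Benefits is conditional and sets no hypothesis. Showing sameness would also need a margin, which adjustment does not supply.

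**Conclusion.** The point holds as a matter of precision and definition on secondary outcomes of a 60-patient pilot. The plan should be amended, but the trial's validity is not in question. The baseline covariate is the clear gain: under equal correlations and a constant effect it beats every unadjusted reading considered, by 6/17/8 points at r = 0.3/0.5/0.7. That gain depends on an effect size and correlations that the documents do not give, and it shrinks to a few points if the baseline correlation is low.

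The unnamed contrast matters whatever the correlation, since the same data can give different conclusions under different readings. Which contrast to name is a trade-off. It would go too far to say that the plan ignores baseline altogether, because one reading of the ANOVA would use it. The primary ADLS-to-cost test and the functional z-score, which is assessed at 5 and 10 weeks only, lie outside this point.

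**What to change.** For each of ADLS, ROM, pain and VR-12:

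- Fit one linear mixed model to the 5-week and final values with arm, visit, arm-by-visit, baseline value and baseline-by-visit. Include all randomised subjects with any follow-up.
- Report the adjusted arm difference with its 95% CI at each visit.
- Name one contrast per outcome, either the adjusted mean of the two follow-ups or the final visit, and give the reason.
- Report the timing of the final visit by arm.
- Drop the normality-based choice of test and keep a rank-based analysis as sensitivity only.
- Claim no error control across outcomes.

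The Statistical Analysis section is written in the past tense. If the data had already been seen, label this analysis post hoc and report it beside the one described there.

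The cost is revised wording and a re-run on data already in the schedule, with no new collection. The named contrast will not be the most powerful in every case: with all correlations 0.3 and a constant effect, choosing the adjusted final visit gives 51% against 66% for the unadjusted mean of the two follow-ups. With an effect at the final visit only, choosing the adjusted mean gives 25% against 51% for the adjusted final visit.
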